
 •Current regular (weekly or more often) practice of meditation or other mind-body intervention •Any major unstable medical/psychiatric illness (e.g., hospitalization within 90 days prior to screening, suicide risk, etc.) •Other non-migraine chronic pain condition (e.g., fibromyalgia, low back pain, etc.) or sensory nerve problems (e.g., neuropathy, Raynaud’s, etc.) •Diagnosis of medication overuse headache (International Classification of Headache Disorders-II) •Volunteers with no pain ratings to frankly noxious stimuli (temperatures > 49°C) or excessive responses to threshold temperatures (~43°C) •Current or planned pregnancy or breastfeeding •Any new medication started within four weeks of screening visit •Unwilling to maintain stable current medication dosages for duration of trial •Failure to complete baseline headache logs

Study Enrollment Procedures

Recruitment: We will recruit 7 participants every 3 months over the 42 month recruitment period. The study will be run in 6 cohorts. Once ~16 participants meet criteria via phone screening, they will be re-evaluated at the in-person screening visit (see below) to ensure they still meet inclusion criteria. After the screening visit, they will begin keeping their 4 week

headache log (see below); once completed, final determination of inclusion and randomization will occur. Recruitment will continue until sample size goals are reached. We will assume ~10% dropout (conservative estimate given our 0% dropout rate in our pilot trial), so will aim to recruit 98 participants for a final sample of 88 participants. (There may be some overlap of the migraineurs with Part 1).

Screening Visit: The study staff will consent participants, confirm migraine diagnosis with history/neurological exam (will include Structured Diagnostic Interview for Headache), and have participants 1) confirm that no pain relieving medications within 12 hours of study visit, 2) complete baseline questionnaires if they have not been completed at home; 3) complete quantitative sensory testing (QST) as described in Part 1; and 4) learn how to capture daily migraine information using REDCap electronic data capture tools (or iPod touches for those without internet access). Participants will track migraines x 4 weeks to 1) confirm diagnosis; 2) confirm ability to log daily; and 3) use as the 4 week “pre-trial” baseline migraine data.

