The Control Group: Migraine/Stress Education: The control group will meet for 8 weeks for 2.5 hours, plus a 1 day learning session. Content will include education about migraine pathophysiology, headache triggers, stress, and gentle stretches. The goal of the control group is to match the time/attention/expectation of the MBSR group, without providing key MBSR active ingredients of mindfulness meditation or yoga. The group will be taught by a health care provider trained in headache care.

Concomitant Interventions

Participants may stay on stable dosages of current migraine medications for the duration of the trial, but will be excluded from starting any new medication within four weeks of screening visit. This makes this study very generalizable to the general population of migraine patients seeking treatment, as most are already on some form of pharmacological treatment and will not need to stop such treatment to participate in the trial. Further, it could be dangerous for a participant to stop migraine medications as it could exacerbate their underlying headache condition.

Adherence Assessment

Adherence to the interventions will be measured by the number of weekly classes/retreat day the participants attend; participants will be considered “completers” of the intervention if they attend at least 5/9 weekly classes/retreat day. Participants who are not able to commit to at least 6/8 classes, and attend the very first class, from the onset of the study will be advised to not participate in the study, so the number of non-completers should be low.

The survey assessments will be completed using REDCap and study personnel will ensure all questions are answered before participants leave each session (See Table 8). Study personnel will also be conducting the QST pain assessments so adherence to both pain testing and survey assessments will be high.

Participants will keep daily headache logs and will receive an email via REDCap with the link to complete these logs. If a participant misses capturing a day of the log, study staff will contact the participant by phone or email and reinforce the importance of completing the daily log. Participants in the MBSR group will also keep track of their assigned home activities with a daily log in a similar way. Participants will also be contacted by phone call, letter, or email for appointment reminders.

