Headache-related Disability -MIDAS-one month		X		X	X	X
HA Management Self – Efficacy		X		X	X	X
Quality of Life-MSQOL, V.21		X		X	X	X
Perceived Stress-PSS-10		X		X	X	X
Depression-PHQ-9		X		X	X	X
Anxiety-GAD-7		X		X	X	X
Hope-Herth Hope Index (HHI)		X		X	X	X
Optimism-Life Orientation Test-revised (LOT-R)		X		X	X	X
NIH PROMIS Sleep Disturbance		X		X	X	X
NIH PROMIS Global Health (first question only)		X		X	X	X
Pittsburgh Sleep Quality Index		X		X	X	X
Social Connectedness Scale – Revised		X		X	X	X
Flourishing Scale		X		X	X	X
Brief Resilience Scale		X		X	X	X
Credibility/Expectation Questionnaire		X		After 2 nd class		

Working Alliance Inventory			After second class	X		
Client Satisfaction Questionnaire				X		
Patient Exit Interview-for Patient Centered Communication Skills			At end of each 8 week class	X		
Class Attendance			During 8 week class			
Home Practice			Begin with 1 st class	Continue	Continue	Continue
Qualitative Interview				X		
Adverse Events			Begin with 1 st class	Continue	Continue	Continue
Allodynia Symptom Checklist		X		X	X	X

FFM-Five Factor Mindfulness Scale
 DERS-Difficulty in Emotion Regulation

Regulation

PCS-Pain Catastrophizing Scale

CPAQ-Chronic Pain Acceptance Questionnaire

HIT-6: Headache Impact Test-6

MIDAS-Migraine Disability Assessment-one month

MSQOL-Migraine Specific Quality of Life, version 2.1

PSS-10-Perceived Stress Scale 10

PHQ-9: Patient Health-related Questionnaire-depression module 9

GAD-7: Generalized Anxiety Disorder 7

Description of Evaluations

Telephone Screen:

A study investigator will contact interested participants for a pre-screening telephone interview. At the beginning of the phone call, potential subjects will be informed of the nature and sensitivity of the questions, asked whether this is an appropriate time for them to answer these questions, and told how long the phone call is expected to take. Participants will be offered the option of completing the pre-screening in person, if they wish and if it is feasible. The pre-screening telephone interview will be performed to explain the protocol, determine eligibility, discuss informed consent, and answer questions. If eligible, they will then be offered participation. Those interested and eligible will be either immediately scheduled for a screening visit or will be called in the future to set it up. A letter will then be sent to them, with the consent form attached for review ahead of time if they would like, in advance of their study visit.

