Follow-up visits will occur immediately after the 8 week class is over, 3 months later and 6 months later. At each follow-up visit, participants will complete the entire instrument assessment and the QST measurements. In addition, at the first follow-up visit, participants will complete a qualitative interview.

Qualitative Interviews: At the initial follow-up, a 30-minute semi-structured interview will be conducted with participants to further explore areas not captured in our standardized quantitative measures. This will be especially important in capturing measures of treatment fidelity not already captured, especially in capturing patient/instructor interactions and enactment of treatment skills.

Reporting Procedures

Plans for ensuring necessary medical or professional intervention in the event of adverse effects to the subjects. [name] is a trained clinician and will oversee the interventions. If a medical emergency arises the appropriate steps will be taken to contact emergency services. At each study visit, the PHQ-9 survey will be scored immediately after completion by the participant. If the participant's responses suggest severe clinical depression, [name] will recommend that the participant see their primary care physician for treatment. If the participant's responses suggest active suicidal ideation, he or she will be sent directly to the emergency department.

We will promptly report any unanticipated problems, serious and unexpected adverse events, deviations or protocol changes to the IRB and Data Safety and Monitoring Board (See Data Safety and Monitoring Board for more details).

Serious adverse events (SAEs) that are unanticipated, serious, and possibly related to the study intervention will be reported to the I-DSMB, Wake Forest School of Medicine IRB, and NCCIH in accordance with requirements.

Unexpected fatal or life-threatening AEs related to the intervention will be reported to the NCCIH Program Officer within 7 days. Other serious and unexpected AEs related to the intervention will be reported to the NCCIH Program Official within 15 days.

Anticipated or unrelated SAEs will be handled in a less urgent manner but will be reported to the I-DSMB, Wake Forest School of Medicine IRB, NCCIH, and other oversight organizations in accordance with their requirements. In the annual AE summary, the I-DSMB Report will state that they have reviewed all AE reports.

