All the secondary outcomes and additional measures will be assessed with these standardized, reliable, well-validated instruments: Five-Facet Mindfulness Questionnaire (mindfulness),^{57,103} DERS (emotion regulation),^{3,104} PCS (pain catastrophizing),^{2,36} Chronic Pain Acceptance Questionnaire (pain acceptance),¹⁰⁵ Herth Hope Index (hope),¹⁰⁶ Life Orientation Test-Revised (optimism),¹⁰⁷ Headache Impact Test-6 (HIT-6) (headache related disability),¹⁰⁸⁻¹¹⁰ Migraine Disability Assessment (MIDAS)-one month (headache related disability),^{111,112} Patient Health Questionnaire-depression module, PHQ-9 (depression),³⁴ Generalized Anxiety Disorder-7, GAD-7 (anxiety),³⁵ Headache Management Self-Efficacy Scale (self-efficacy),¹¹³ Migraine Specific Quality of Life Questionnaire, version 2.1 (MSQv2.1) (quality of life),^{114,115} the Perceived Stress Scale 10, PSS (perceived stress),¹¹⁶ the Brief Resilience Scale, the Resilience Scale for Adults, the Flourishing Scale, the Social Connectedness Scale-Revised (SCS-R), the Pittsburgh Sleep Quality Index, the Allodynia Symptom Checklist (ASC-12), and well-validated NIH Patient Reported Outcomes Measurement Information System (PROMIS) measures of sleep, fatigue, pain interference, satisfaction with participation in social roles, and global health. Changes from baseline to initial follow-up will be primary outcomes; secondary outcomes will include changes from baseline to follow-ups at 3 and 6 months.

Additional Information Collected

Sociodemographic and clinical information will be collected at the screening visit.

Expectations for improvement: Expectations can impact results.^{39,117} At baseline and after the second session, participants will rate their expectations using the Credibility/Expectancy Questionnaire.⁹⁶

Class Attendance and Home Practice: Participants in both groups will track their home activities up to the 6-month follow-up visit via REDCap logs and the instructors will track patient class attendance.

Qualitative Interviews: At the initial follow-up, a 30-minute semi-structured interview will be conducted with participants to further explore areas not captured in our standardized quantitative measures.

Data Analyses

Analysis 2a: The probability that an individual experiences a migraine on any given day will be examined as a function of group (MBSR vs. control) and treatment phase. A statistically significant group x phase interaction will be interpreted as evidence that treatment differentially

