
impacted the daily probability of migraine. This effect size will be indexed by converting the daily probability to headache counts as recommended for clinical trials in headache.¹¹⁸ If necessary we will model change using polynomial trajectories (i.e., growth curves) to better fit the time-course of treatment.

Analysis 2b: To examine this hypothesis, we will conduct an ANCOVA with pain unpleasantness at post-treatment as the dependent variable, group as the independent variable, and pain unpleasantness at pre-treatment as the covariate.

Analysis 2c: This analysis is identical to 2b, with the appropriate outcomes.

Analysis 3a: Baseline levels of pain catastrophizing and emotional reactivity will be used as predictors in the multilevel models predicting the trajectory of migraine attacks over the course of treatment.

Analyses 3b: This analysis is similar to 3a, except that changes in mindfulness (i.e., change scores from pre-treatment to post-treatment) will be used as predictor of migraine trajectory.

DATA COLLECTION AND QUALITY ASSURANCE

Data Collection Forms

Information will be collected from REDCap daily headache logs for appropriate diagnosis of migraines during an initial 4 week period prior to randomization and participants will continue to track daily headaches for the duration of the trial. Ipod touches with Pendragon software will be available to those without internet access and unable to use REDCap from home. Experimental heat measurements will be conducted at baseline and at each of the 3 follow-up evaluations. Participants will also complete standardized questionnaires using REDCap at baseline and at each of the 3 follow-up evaluations with an option to complete these questionnaires at home prior to the visit. In addition, a 30 minute qualitative interview will be conducted at the first follow-up visit to evaluate the participants' experience with the interventions. Each interview will be audiotaped. Socio-demographic and clinical information will also be collected at the screening visit.

Description of data that will be recorded on human subjects. Each 30 minute qualitative interview of the migraine and control subjects will be audiotaped and then transcribed. Participants will be photographed one of the study visits. These photos will be stored on the study's secure Ishare. Each subject will have provided informed consent to perform this.

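### Part 2's response to suicidal ideation relies on scoring the PHQ-9 at the visit, yet the home-completion option does not exempt the PHQ-9, so a home answer could be held unread until the visit.

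*Combined protocol and SAP*

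**What the plan says.** **Safety rule.** Part 2, Reporting Procedures (under Follow-up Visits) states: "At each study visit, the PHQ-9 survey will be scored immediately after completion by the participant". Severe depression leads to advice to see the primary care physician. For the urgent case, if the participant's "responses suggest active suicidal ideation, he or she will be sent directly to the emergency department".

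**Home option.** Part 2, Data Collection Forms says the standardized questionnaires are completed in REDCap "at baseline and at each of the 3 follow-up evaluations with an option to complete these questionnaires at home prior to the visit". The Screening Visit paragraph under Study Enrollment Procedures agrees for baseline: participants are to "complete baseline questionnaires if they have not been completed at home".

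**Scope.** Table 8 has a row for "Depression-PHQ-9", marked at baseline, initial follow-up, 3 months and 6 months. The Part 2 Outcomes section also lists the PHQ-9 among the standardized instruments.

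**Text pointing to on-site completion.** The Follow-up Visits section says: "At each follow-up visit, participants will complete the entire instrument assessment and the QST measurements". The Baseline Visit description places the instruments at step C, after consent at step A.

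**The concern.** The protocol treats active suicidal ideation as needing action on the spot. That works only if the participant answers while staff are present to score the form. The home option separates answering from scoring, and nothing in its wording keeps the PHQ-9 out.

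At stake is a disclosure of suicidal ideation sitting in the study database with nobody assigned to read it before the participant arrives. If the visit is postponed, the wait grows. If the participant never attends, no scoring point is stated at all.

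**Working it through.** The plan gives no figure on this point, and the only arithmetic is a count of time points. The check is a comparison of the texts.

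1. **Is the PHQ-9 inside the home option?** The option applies to the standardized questionnaires as a set. Outcomes places the PHQ-9 in that set. Table 8 schedules it at 1 baseline + 3 follow-ups = 4 assessments, the same 4 that the option covers. Neither statement of the option exempts any instrument.

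2. **Can the safety rule be met for a home form?** The rule has two parts: scoring happens at the visit, and it happens as soon as the form is finished. For a form finished at home, scoring at the visit is not immediate. Immediate scoring would have to be remote, and no remote step is described: no alert, reviewer, time limit or call-back. The two provisions cannot both be followed for a home PHQ-9.

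3. **Does another stated safeguard close the gap?**
   - Adherence Assessment says "study personnel will ensure all questions are answered before participants leave each session". This is a completeness check made at the session, not a review of risk.
   - The phone or email contact in the same section concerns missed daily headache logs.
   - The provision for contacting emergency services operates once an emergency is known. An unread answer is not known.
   - Suicide risk is an exclusion in Table 5, which screens at entry and does not cover ideation arising later. Table 5 also has no PHQ-9 cut-off, whereas Part 1 excludes scores above 20.
   - Both parts refer to a separate DSMB plan, which was not among the documents.

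4. **How long could an answer wait?** No maximum interval between home completion and visit is given. At baseline, step B reschedules anyone who arrives with a headache, in a population with 4-20 migraine days per month, so the interval can lengthen.

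5. **Does home completion at baseline come before consent?** The Baseline Visit text takes consent at the start of that visit, and Part 1's Informed Consent Forms section requires consent before any phase. But the Screening Visit paragraph lists consent first and does not say when the home forms are done. Someone who consented, was rescheduled for headache and filled in the forms before returning would fit the text. Part 1 participants who continue into Part 2 would already have signed a consent, though whether it covers the Part 2 forms cannot be seen. The text therefore leaves the order open.

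**The case against.** The best reply is that the specific rule governs the general one. Reporting Procedures contains the only procedure written for the PHQ-9. Since no remote scoring is described, it can be satisfied only by completing the form on site. The Follow-up Visits sentence and the order of the Baseline Visit steps support that reading. On it, staff who accept an unscored home PHQ-9 are departing from the protocol. This reading is reasonable, and it means the documents show two rules in conflict rather than a settled decision to leave home answers unread. It does not remove the problem: staff working from the Screening Visit or Data Collection Forms text would find nothing to stop them offering a home PHQ-9.

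A second objection is that moving the PHQ-9 to the visit does not bring detection forward: an attending participant's ideation is still first learned of at the visit. That is correct, and it limits what the fix can claim.

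A reader might infer three stronger points that the documents do not support:

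- **That participants complete baseline forms before consenting.** As step 5 shows, this is only a possibility.
- **That the exposure is capped at 98 x 4 = 392 forms.** The 98 are those randomized. Baseline forms are completed before the 4-week log that decides inclusion, so people who are screened but not randomized complete them too. A count of forms would in any case not be a count of events.
- **That a known proportion of participants is at risk.** The documents give neither the share of forms done at home nor the frequency of answers needing a response.

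**Conclusion.** The concern holds as a conflict between two stated rules on a suicide-risk step, and the protocol should be corrected. As written, a home PHQ-9 showing suicidal ideation could be held unread until the visit, at any of the 4 scheduled Part 2 assessments. Neither its frequency nor the length of the delay can be estimated from the documents.

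The conclusion assumes that the home option means what it says for every questionnaire in the set, and that no remote review is specified elsewhere. The unseen DSMB plan could change the second assumption, so confidence is medium. The entry exclusion for suicide risk and the clinician's oversight lower the starting risk but do not resolve the conflict. The timing of consent is a secondary clarification only.

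**What to change.** Add one sentence to both the Screening Visit paragraph and Data Collection Forms: *The PHQ-9 is completed at the visit (at baseline, after consent) and scored before the participant leaves.* The other follow-up questionnaires can stay on the home option.

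The benefit is that the study no longer holds an unread disclosure, and the answer that is scored is current and given with staff present. Earlier detection would need something different: a home PHQ-9 with an automatic alert, a designated clinician role, a review time limit and a call-back procedure. That is a workable alternative, but it requires more procedure.

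As a separate clarification, state in the Screening Visit paragraph that baseline questionnaires may be done at home only after the consent form is signed.

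The PHQ-9 change costs a few minutes at a visit that takes place anyway. The consent clarification would lengthen the baseline visit for anyone who would otherwise have completed the forms before signing. Neither change alters an endpoint, the sample size or the visit schedule.
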